### **2.3.2 Potential Benefits**

Participants may benefit from the SDF and ART + FV treatment applications in the arrest of caries and in patient-reported pain and oral health quality of life symptoms. Society may benefit from the knowledge gained about the comparative effectiveness of a simple topical medical treatment (SDF) versus a typical dental treatment. The findings from the proposed study will be useful for patients and providers. Patients can make informed decisions regarding the evidence-based non-surgical options that are available for treating decay, reducing tooth pain, and improving quality of life.

Providers will use the findings to establish standard of care for older adults with unique dental issues, co-morbid conditions, frailty, and dementia. Long-term having an effective standard of care will reduce oral health disparities for older adults with limited resources. Further, delivering dental care in community-based settings will be instrumental in treating far more older adults than the current dental office-based care. This will address the national disparity gap and the limited dental insurance options for older adults.

There will be no direct benefit to the participants in the focus groups, but taking part in group discussions could have indirect or incidental benefits for respondents. These might include the social stimulation of the discussion process, or the knowledge that their participation could help in disseminating the findings to other populations.

Older adult respondents will receive a tooth care kit (free toothbrushes, toothpaste, floss) to facilitate good oral hygiene. On balance, we believe any potential risks are reasonable in relation to the anticipated benefits to research participants and others.

### 3 OBJECTIVES

#### 3.1 Study Objectives

Primary objective:

- 1) To investigate the comparative effectiveness of two evidence-based strategies in low-income older adults  $\geq 62$  years old followed for one year: (Arm 1) a “simple medical” strategy of bi-annual topical application of silver diamine fluoride (SDF) versus (Arm 2) a “typical dental” strategy consisting of atraumatic restorative treatment (ART) + bi-annual application of fluoride varnish (FV).
- 2) To examine the narratives of subgroups of publicly subsidized housing participants to understand their experiences with non-surgical regimens and identify ways to improve and disseminate in other community-based settings nationally.

#### 3.2 Study Outcome Measures

##### 3.2.1 Primary Outcome Measures

Primary outcomes are: (1) participant reported outcomes including tooth pain and hypersensitivity, and (2) clinical outcomes (caries arrest). Clinical outcomes will be assessed through dental exams conducted by calibrated examiners. Participant questionnaire will assess patient-reported outcomes using validated instruments. All primary outcomes will be measured at baseline, 26 & 52 weeks.

##### 3.2.2 Secondary Outcome Measures

Secondary outcomes are: participant reported outcomes (oral health quality of life); and clinical (prevention of new decay). All secondary outcomes will be measured at baseline, 26 & 52 weeks.

##### 3.2.3 Mediators, Process Outcomes

Moderator variables are: socio-demographics, medical/physical conditions, oral health behavior that will be collected at baseline (prior to treatment).

Process outcomes are: Safety measure that will be collected at 2, 26 & 54 weeks, and satisfaction survey with the treatment will be assessed at 54 weeks.

## 4 STUDY DESIGN

This study is a cluster randomized clinical trial to assess the comparative effectiveness of two caries treatment interventions for individuals residing in 22 publicly subsidized housing facilities/sites (HUD Section 202) and other low-income housing voucher programs in NE Ohio (**RQ-2**). Each facility will be randomized to 2 arms:

Arm 1 (11 facilities) – A total of 275 participants from these facilities will receive biannual SDF.

Primary Hypothesis: Simple medical treatment (Arm 1) is non-inferior to typical dental treatment (Arm 2) for clinical (caries arrest) and patient-reported (tooth pain/hypersensitivity) at 12-months post treatment.

Arm 2 (11 facilities): A total of 275 participants from these facilities will receive ART + biannual FV application.

Secondary Hypothesis: Simple medical treatment (Arm 1) is non-inferior to typical dental treatment (Arm 2) for clinical (new decay) and patient-reported (oral health quality of life) outcomes at 12-months post treatment.

The participants will be recruited over a *three*-year period, and each participant will be followed for one year (total of 3 visits -baseline, 26 weeks, 52 weeks). All participants will receive a dental screening and prophylactic cleaning at all visits. The proposed interventions will address the high burden of untreated tooth decay in community dwelling low-income older adults and thus reduce disparities (**RQ-5**). The non-surgical interventions can be provided by paraprofessionals. We have previously worked in these housing facilities and understand the logistics of recruiting and conducting clinical dental exams on-site (**PC-1**).

The randomization is at the level of the cluster (housing facility) for logistical efficiency. This will greatly reduce the potential for error that could otherwise occur with people at the same site assigned to different treatments. Furthermore, keeping the same treatment at each site reduces chances of 'contamination' (i.e. participant discussing their treatment with others). Additionally, stratified cluster randomization will be used, i.e. a block (constrained) randomization approach in which balance over treatments is assured for 2 key cluster-level (stratification) variables, namely facility size ( $>100$  versus  $\leq 100$  residents), and geographic location (Cuyahoga County vs other (**RQ-5, RC-2, RC-5**)).

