### 11.2 Sample Size Considerations (RC-3)

For continuous outcomes we computed power using a variance correction (i.e., variance inflation factor) to take into account possible correlations of outcomes within cluster. All computations of required effective samples sizes (or corresponding power) were done using the PASS 2005 software. For binary outcomes, we used a specialized program for cluster randomization (a non-inferiority test comparing two proportions).

The primary outcome tooth pain was defined as change in pain (based on a 100-mm visual analogue pain scale (VAS), where higher is worse pain) from baseline to 1 year. We assume a mean difference of 0 between SDF and ART+FV, and consider non-inferiority to be within a margin (mean difference) of 8 between SDF and ART+FV arms; and based on prior literature also assume a common standard deviation of 25. Further, we assumed an average of 25 subjects recruited per site, an intraclass correlation (ICC) of 0.01 (based on prior studies and literature), and a 15% dropout rate (based on prior studies). The use of a 0.025 alpha-level one-sided t-test to test the null hypothesis of inferiority versus the alternative hypothesis of non-inferiority (as defined above), 11 sites per treatment group (corresponding to 275 subjects per treatment group or 550 total) will provide an estimated 89% power to conclude non-inferiority. Even if the ICC is higher (0.02), there will still be 83% power to detect non-inferiority.

A second primary outcome is arrest rate. Previous data show a high arrest rate (of around 90%) for ART + FV. We expect a similar arrest rate for SDF. For the power calculation we suppose the unit of analysis to be the person, and consider the binary outcome of 'arrest' defined as all lesions for an individual being arrested. We assume equal (person-level) arrest rates of 90% for the ART+FV and SDF groups, and consider non-inferiority to be within a margin (difference in arrest proportions for ART+FV versus SDF) of 0.09. With the same assumptions as before using a 0.025 alpha level one-sided z test, the targeted sample size of 275 subjects in 11 sites per treatment group will provide an estimated 85% power to conclude non-inferiority. For a higher ICC of 0.02, there will still about 80% power to detect non-inferiority.

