## 11.4 Final Analysis Plan (IR-1, RC-4)

Each primary outcome will be compared between the SDF and ART+FV groups. For tooth pain, a 95% confidence interval (CI) based on a t-test for the difference in mean responses (SDF minus ART+FV) will be computed. If this confidence interval lies within the interval  $(-\infty, 8)$  we may conclude 'non-inferiority' of SDF relative to ART+FV treatment. The confidence interval may secondarily be examined to assess possible superiority of one intervention over the other. For arrest rate, a 95% CI for the difference in rates (based on a z statistic) will be computed. If this confidence interval lies within the interval  $(-0.09, 1)$  we may conclude 'non-inferiority' of the SDF relative to ART+FV treatment. As above, possible superiority of one intervention over the other may also be assessed. For other outcomes, we will also compute 95% CI for differences in means (or proportions for binary outcomes). These secondary outcomes will be assessed in an exploratory manner for possibly superiority or inferiority based on appropriate margins.

We will seek to corroborate initial results using a generalized estimating equations (GEE) approach. For each outcome we will fit a GEE (marginal) model that includes a treatment indicator and prognostic variables (including sociodemographic variables, medical conditions, and oral health behaviors). Appropriate link functions (e.g., logit link for binary outcomes and identity link for continuous outcomes) will be specified and an exchangeable working correlation matrix used to allow for correlations within site. The arrest outcome will be analyzed as a binary outcome (as described in the sample size section), and secondarily as the number of arrested lesions assuming an appropriate distribution (e.g., negative binomial) and link function (e.g., log link). Robust t tests with correction for a small number of clusters will be used to test for treatment effects and corresponding 95% confidence intervals computed.

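### One primary hypothesis spans two primary outcomes with no success rule: joint power is unstated, and either interval alone can support a non-inferiority conclusion

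*Combined protocol and SAP*

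**What the plan says.** Section 4 gives a single primary hypothesis, that SDF "is non-inferior to typical dental treatment (Arm 2) for clinical (caries arrest) and patient-reported (tooth pain/hypersensitivity) at 12-months post treatment". Section 11.1 likewise states one hypothesis covering both primary outcomes, and lists the secondary outcomes in the same sentence.

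Section 11.2 powers the two outcomes one at a time. For pain, "The use of a 0.025 alpha-level one-sided t-test" with 275 participants in 11 sites per arm "will provide an estimated 89% power to conclude non-inferiority", falling to 83% at an ICC of 0.02. Arrest is introduced as a second primary outcome and is powered "using a 0.025 alpha level one-sided z test" at 85%, or about 80% at an ICC of 0.02. No power is given for succeeding on both.

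Section 11.4 says "Each primary outcome will be compared between the SDF and ART+FV groups". It then gives each outcome its own rule: the pain CI must lie below 8, and the arrest CI must lie above -0.09. Each rule, taken alone, permits a conclusion that SDF is non-inferior to ART+FV. Only the other, secondary outcomes are described as exploratory. Nowhere is there a rule for combining the two results, a testing order, an alpha split or any other multiplicity control for the primary outcomes.

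**The concern.** A single hypothesis tested through two separate rules can be declared met in two ways, and the protocol does not choose between them.

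- If both outcomes must clear, each test can stay at one-sided 0.025. The chance of success is then the joint power, which is lower than either figure printed in Section 11.2.
- If one outcome is enough, the single-outcome powers understate the chance of a claim. SDF also has two chances to be called non-inferior, so the overall one-sided error exceeds 0.025.

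These consequences are alternatives and do not apply together. A split result, with pain clearing and arrest not, or the reverse, has no pre-specified interpretation, so the reading could be chosen after the results are known. That matters because Section 2.2 presents the trial as informing a standard of care.

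**Working it through.** **Inputs, all from Section 11.2.** Pain: "We assume a mean difference of 0 between SDF and ART+FV", "consider non-inferiority to be within a margin (mean difference) of 8 between SDF and ART+FV arms", SD 25. Arrest: 90% in both arms, margin 0.09. Common to both: 25 recruited per site, 11 sites per arm, 15% dropout, ICC 0.01 (0.02 as the less favourable case), one-sided 0.025.

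**Step 1. Reproduce the stated powers.**

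- Evaluable per arm: 275 × 0.85 = 233.75. Per site: m = 25 × 0.85 = 21.25.
- Design effect = 1 + (m - 1) × ICC. At ICC 0.01 it is 1 + 20.25 × 0.01 = 1.2025, so effective n = 233.75 / 1.2025 = 194.4 per arm. At ICC 0.02 it is 1.405, so effective n = 166.4.
- Power = Φ(margin / SE - 1.96).
- Pain, ICC 0.01: SE = 25 × √(2/194.4) = 2.536; 8 / 2.536 = 3.155; Φ(1.195) = 88.4% (stated 89%).
- Arrest, ICC 0.01: SE = √(2 × 0.9 × 0.1 / 194.4) = 0.0304; 0.09 / 0.0304 = 2.958; Φ(0.998) = 84.1% (stated 85%).
- ICC 0.02, same steps: pain 83.1% (stated 83%), arrest 78.1% (stated about 80%).

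All four agree with the protocol to within 2 percentage points, so the method is close enough to the one used there.

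**Step 2. Power if both outcomes are required.** Under independence this is the product of the two powers: 0.884 × 0.841 = 0.743 at ICC 0.01 and 0.831 × 0.781 = 0.649 at ICC 0.02. With positive correlation between the two test statistics it is a bivariate normal probability. The protocol gives no correlation, so a range is assumed:

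| Design | ICC | Pain alone | Arrest alone | Both, r = 0 | Both, r = 0.5 | Both, r = 0.8 |
|---|---|---|---|---|---|---|
| 550, 22 sites | 0.01 | 88.4% | 84.1% | 74.3% | 77.5% | 80.5% |
| 550, 22 sites | 0.02 | 83.1% | 78.1% | 64.9% | 69.4% | 73.4% |
| 590, 26 sites | 0.01 | 90.9% | 87.1% | 79.1% | 81.6% | 84.1% |
| 590, 26 sites | 0.02 | 86.6% | 82.0% | 71.0% | 74.6% | 78.0% |
| 590, 33 sites | 0.01 | 91.8% | 88.2% | 81.0% | 83.1% | 85.4% |
| 590, 33 sites | 0.02 | 88.5% | 84.2% | 74.6% | 77.7% | 80.7% |

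Starting from the printed powers instead gives 0.89 × 0.85 = 75.7% at ICC 0.01 and 0.83 × 0.80 = 66.4% at ICC 0.02 under independence. Whatever the correlation, joint power cannot exceed the smaller single-outcome power.

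The 590 rows add the 40 participants described in the Protocol Summary and Section 4.2 and keep 15% dropout. Evaluable per arm is 295 × 0.85 = 250.75, with 501.5/26 = 19.3 or 501.5/33 = 15.2 per site. Two site counts are shown because Section 4.2 adds 4 sites (26 in total), while the Protocol Summary and Table 1 add 11 (33 in total). Section 11.2 was not updated for either.

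**Step 3. Error if either outcome suffices.** With SDF exactly at the margin on both outcomes and independent tests, the error is 1 - 0.975² = 4.94%. It is 4.8% at correlation 0.3, 4.5% at 0.5 and 3.9% at 0.8.

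**The case against.** The best defence is that the protocol intends two separate questions. Section 3.2.1 lists primary outcomes in the plural, Section 11.2 powers them one at a time, and Section 11.4 draws a conclusion from each. On that reading 89%, 85% and one-sided 0.025 all apply as printed, and Section 11.2 claims neither a joint power nor a familywise rate.

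The conjunction in Section 4 is also weak evidence of a both-required rule. The secondary hypothesis there is joined in the same way, yet Section 11.4 treats secondary outcomes as exploratory. A reader might infer that the protocol requires both outcomes. It does not say so.

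Much of this stands: the single-outcome powers are sound as such, and the both-required rule is an inference. It does not remove the gap. Sections 4 and 11.1 write one hypothesis, Section 11.4 lets either interval support non-inferiority of SDF, and nothing says that error is controlled per outcome only. If separate claims are intended, that also has to be stated.

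A further caution is that the pain power uses a 100-mm VAS, whereas Table 8.1.1 and Appendix A list PROMIS Pain Intensity 3a and the Dental Discomfort Questionnaire. The joint figures inherit those VAS inputs and may not describe the pain scores actually collected.

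**Conclusion.** The point holds as an unspecified success rule with a quantifiable effect. If both outcomes are required, joint power is about 74-81% at ICC 0.01 and 65-73% at ICC 0.02 for the original design. With 590 participants in 26 to 33 sites it is about 79-85% and 71-81%. These ranges assume a correlation of 0 to 0.8, the Section 11.2 inputs and 15% dropout. The larger-enrolment figures may be generous, because the 40 were added after about 40 participants missed the 26-week visit.

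If either outcome suffices, the one-sided familywise error is up to 4.9%.

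Three stronger readings are tempting and not supported:

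- That 89% and 85% are wrong. They reproduce as single-outcome powers.
- That the trial has 74% power. That is the independence end of the range for the design before enrolment was increased.
- That the error rate is 5%. The figure near 5% is a ceiling, reached only with SDF at the margin on both outcomes and essentially uncorrelated tests.

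**What to change.** In Sections 11.1 and 11.4, before the outcome data are analysed, state that the primary hypothesis is met only if both 95% CIs clear their margins. State also that one outcome clearing alone is reported as an outcome-specific result and not as the primary hypothesis met. The tests, margins and alpha stay as they are, and no alpha split is needed.

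In Section 11.2, label 89% and 85% as single-outcome powers. Add the joint power as a range over the assumed between-outcome correlation, for the current enrolment and a single reconciled site count.

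The cost is a few sentences and a less favourable power figure for the primary claim. No new data or participants are needed. For comparison, letting either outcome suffice with the error held at 0.025 by a Bonferroni split (0.0125 each) would lower the single-outcome powers in the original design at ICC 0.01 to 81.9% for pain and 76.3% for arrest.

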### 4.1 Study Participants (RQ-3, RQ-4, PC-2)

Subjects will be low socioeconomic status (SES) adults  $\geq 62$  years of age in NE Ohio counties (Cuyahoga, Lorain, Summit, Ashtabula, Geauga, and Lake) residing in 22 participating HUD Section 202 and other publicly subsidized housing facilities (see table 1). The population is diverse: African American/Black, Caucasian/White including Hispanic/Latino, and Asian. Medicaid participation among the tenants is 76% among facilities. From our prior study in these facilities, mean age is 74 years, 76% female, 51% Caucasian, 45% African-American, 2% Hispanic, and 2% other racial/ethnic groups; 60% of HUD older adults had none/rare dental visits in over 3 years. The study will be offered to all older adults if they are aged  $\geq 62$  years, reside in the 22 housing facilities, have at least one natural tooth and be willing to stay in the

study for 1 year. Only those with severe medical, cognitive or motor impairments will be excluded. To be eligible for enrollment in the clinical trial phase of the study, at the baseline dental exam, subject must have at least one untreated active root or coronal carious lesion with ICDAS-II lesion severity code of 3 or greater.

Table 1. Facilities Enrolled in the Clinical Trial				
Facility Name*	# of tenants	Name of Individual Providing Letter of Support (Agency)	Type of Community	County
Westerly Apartments	455	[name] (Westerly Apartments)	suburban	Cuyahoga
St. Timothy Manor	40	[name] (Humility of Mary Housing)	suburban	Cuyahoga
St. Timothy Park	40	[name] (Humility of Mary Housing)	suburban	Cuyahoga
Villa at Marion Park	40	[name] (Humility of Mary Housing)	urban	Summit
St. Patrick Manor	50	[name] (Humility of Mary Housing)	suburban	Lorain
Jennings Manor, Library Court, St. Rita, St. Agnes	220	[name] (Jennings)	suburban	Cuyahoga
Margaret Wagner	60	[name] (Benjamin Rose Institute)	urban	Cuyahoga
Willowood Manor	74	[name] (Willowood Manor)	suburban	Cuyahoga
Knickerbocker	168	[name] (Knickerbocker)	suburban	Cuyahoga
Abington Arms	157	[name] (Abington Arms)	urban	Cuyahoga
Fedor Manor	145	[name] (Fedor Manor)	suburban	Cuyahoga
Ambleside Tower	201	[name] (CMHA)	urban	Cuyahoga
Severance Tower	188	[name] (CMHA)	urban	Cuyahoga
Cedar Highrise	155	[name] (CMHA)	urban	Cuyahoga
Addison Square	225	[name] (CMHA)	urban	Cuyahoga

[figure not shown]
Apthorp Tower	166	[name] (CMHA)	urban	Cuyahoga
Euclid Beach Gardens	149	[name] (CMHA)	urban	Cuyahoga
Bohn Tower	267	[name] (CMHA)	urban	Cuyahoga
Riverview Tower	498	[name] (CMHA)	urban	Cuyahoga
King Kennedy	91	[name] (CMHA)	suburban	Cuyahoga
Quarrytown	180	[name] (CMHA)	suburban	Cuyahoga
Franciscan Village	180	[name] (Franciscan Village)	urban	Cuyahoga
Total # of Tenants	3749			
*Average Medicaid: 76%				
Additional 11 sites added with modification				
Carnegie Tower at Fairfax	171	[name]	Urban	Cuyahoga
Mother Teresa Manor/Commons	99	[name]	Suburban	Cuyahoga
Educator Senior Housing	112	[name]	Urban	Cuyahoga
Lorain Square	110	[name] (CMHA)	Urban	Cuyahoga
Beachcrest	235	[name] (CMHA)	Urban	Cuyahoga
Villa Serena	242	Vesta Corp MOU	Suburban	Cuyahoga
Helen S. Brown	64	[name]	Urban	Cuyahoga
Greater Abyssinia Tower	69	[name]	Urban	Cuyahoga
Mt. Auburn Manor	107	[name] (CMHA)	Urban	Cuyahoga

Mildred Brewer	39	[name] (CMHA)	Urban	Cuyahoga
La Ronde	57	[name] (CMHA)	Urban	Cuyahoga

The 22 housing facilities for this study are located in Northeast Ohio counties. We have formed relationships with administration of HUD and Regional Housing Authorities to ensure these sites are available. All 22 facilities were carefully chosen to ensure accurate representation of the northeast Ohio region. Twelve facilities are located in large metropolitan areas, while 6 are in inner ring and 4 are in outer ring suburbs or rural areas. All facilities are publicly subsidized through United States Department of Housing and Urban Development (HUD) programs geared toward seniors with limited financial resources. Several public and private housing authorities and management agencies oversee the facilities in our sample, each with multiple housing units located throughout the northeast Ohio region. This network of agencies will be of value when communicating results and for possible further implementation.

#### 4.2 Model and Design

Figure 4.2.1 shows the study model for the intervention. The comparative effectiveness of “simple medical”, i.e. SDF versus “typical dental”, i.e. atraumatic restorative treatment (ART) + fluoride varnish (FV) intervention in this study is focused on the person level to address the unique oral health needs of low-income older adults. Figure 1 indicates that the proposed intervention is hypothesized to arrest caries in older adults with untreated caries and prevent tooth pain/hypersensitivity (primary outcomes); prevent new decay and improve oral health-related quality of life (secondary outcomes) over a 12-month follow-up period. Safety and satisfaction measures are process outcomes that are critical to assess for sustainability and dissemination of the interventions. Factors likely to moderate the effectiveness of interventions are socio-demographics, chronic medical conditions, and oral health behavior. These baseline (pre-treatment) variables are also considered as prognostic variables (related to outcomes). Additionally, 3 focus groups ( $\approx$  8 to 10/group) of study participants in years 2, 3, and 4 will be conducted to understand experience with treatment and find ways of improvement.

